To try to reverse this situation of dysbiosis, one possibility would be the use of prebiotics, which have the potential to stimulate the growth of beneficial intestinal bacteria selectively (5); such as *F. prausnitzii*, which is a butyrate producer apart from being one of the three most abundant species in a healthy human intestine (6). The importance of the abundance of butyrate-producing species in the intestinal microbiota lies in the anti-inflammatory activity of this compound (7)

Among the wide variety of prebiotic foods, in this case we are interested in a common food in the Mediterranean diet, in order not to excessively change the diet of patients. Bread is a potentially prebiotic food that has a significant percentage of insoluble dietary fibre. Dietary fibre induces the production of short-chain fatty acids, basically acetic, propionic and butyric, which are important nutrients for epithelial cells and intestinal microbiota. Therefore, it has the ability to promote the growth of butyrate-producing bacteria in the intestinal microbiota (3). A quality bread, made with compact and long-fermented sourdough, could have beneficial prebiotic effects both for the general population and for those patients with UC in remission, but who continue to present symptoms compatible with Irritable Bowel Syndrome. If the prebiotic effect of these breads were confirmed, they could even be recommended by health agents to the general population as prevention or relief of symptoms caused by intestinal inflammation.

Thus, from the perspective of public health and as a personal interest of our group in collaboration with ELIAS FORNER S.L., we believe it would be interesting to better understand the impact of bread on the microbiota-inflammation relationship of the intestinal mucosa; and if the intake of breads made in a traditional way, with sourdough and long fermentation, could be an advantage for our study population.

2. HIPOTHESIS AND OBJECTIVES

2.1 Hipotesis

The intake of bread produced following traditional breadmaking techniques is beneficial for people with quiescent Ulcerative Colitis (UC), but who present symptoms compatible with Irritable Bowel Syndrome (IBS), through the modulation of its intestinal microbiota.

2.2 Objectius

To compare in vivo the influence of 2 types of bread, one long-fermented and one short-fermented, on the clinic and intestinal microbiota of patients with quiescent Ulcerative Colitis (UC), with symptoms compatible with IBS (Rome IV Criteria).

Specific objectives:

- To determine changes in the overall gut microbiota composition in patients with quiescent UC, before (V0) and after 8 weeks (VF) of the intake of traditional bread.
- To determine the correlation between the changes observed in the composition of the intestinal microbiota in V0 and VF and the clinical condition of the patient with quiescent UC.
- Assess the impact of traditional bread versus modern bread on improving the clinical response of patients with quiescent UC.

3. MATERIALS AND METHODS

3.1. Type of study

Randomized, double-blind, prospective clinical trial

3.2. Inclusion criteria

- > 18 years of age
- Patients diagnosed with ulcerative colitis according to established clinical and histological criteria as common clinical practice
- Remission of ulcerative colitis defined as a total Mayo score ≤ 2 and faecal calprotectin values under 250 ng/g
- Moderate-to-severe IBS-like symptomatology defined by Rome IV criteria and IBS Symptom Severity Score (IBS-SSS) > 175

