3.3. Exclusion criteria

- Presence of flare-up of UC (Index de Mayo ≥ 2 , Calprotectin ≥ 250 ug/gr)
- Coeliac disease, colectomy, or intestinal resection
- Antibiotic intake, prebiotic or probiotic treatment within 3 months before the study
- Any malignancy, pregnancy, or breastfeeding
- Intake of medication potentially influencing gastrointestinal function
- Disability to give informed consent

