3.6. Variables

a) Demographic variables

- **Age** expressed in years (y)
- **Sex** Male (M)/ Female (F)
- **Weight** expressed in IMC
- **Ethnic**: Caucasian/ African/ Asiatic/ American
- **Tobacco**: YES / NO / EX-Smoker
- **Age of UC diagnosis** expressed in years (y)
- **Familiar Antecedents** (YES/NO) which kind of disease?

b) Clinical variables:

- **Mayo Clinical Score** (*Clinical colitis activity index*) (Schroeder KW *et al.*

NEngl J Med 1987; 317: 1625-9). Punctuation range: 0-9 punts.

- **Rome IV Criteria** (Lacy BE, Mearin F, Chang L, *et al.* Bowel disorders. *Gastroenterology* 2016;150:1393-407).

- **IBS- SSS** (*Irritable Bowel Syndrome – Symptom Severity Score*) (Almansa C *et al.* *Rev Esp Enferm Dig* 2011 Dec;103 (12):612-8.

- **HADS** (*Hospital Anxiety and Depression Scale*) (Johnston M, *et al.* *J Psychosom Res* 2000;48:579-84.9)

- **Escala de Likert**: Subjective valuation of improvement of symptoms after the intervention

- **Adherence to Mediterranean Diet Questionnaire** (Estruch R *et al* *NEJM* 2013).

c) Analytical parameters:

Haemoglobin: blood haemoglobin concentration (g/dl).

Albumin: blood albumin concentration (g/dl).

Triglycerides: blood triglycerides concentration (mg/dl).

Cholesterol: blood cholesterol concentration (mg/dl).

C-reactive protein: blood C-reactive protein concentration (mg/dl).

Faecal calprotectin: faecal calprotectin concentration (µg/g).

d) Variables Microbiològiques

The microbiological profile of the microbiota of these patients will be analysed through high-throughput sequencing before and after the intervention.

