3.7. Methods

The proposed study will include 96 patients with UC in remission (Mayo Index ≤ 2 and Calprotectin ≤ 250 µg/gr), over 18 years of age, who have signed informed consent, who meet Rome IV criteria and present a moderate-severe severity index will be included (IBS-SSS >175). These patients will be randomized to one of the two intervention arms (N=48 per group):

- Treatment group: traditional bread (200g daily).
- Control group: modern bread (200g daily).

For both intervention groups stool and blood samples will be collected before starting the intervention (Visit 0 - Basal), and then after 8 weeks (Final Visit). The monitoring period will be 8 weeks. In addition, we will collect demographic data (age, sex, smoking habit, etc.), clinical data (Mayo index, Rome IV, IBS-SSS, CVE 20, HADS, PCR Likert scale, VSG, albumin, hemoglobin, faecal calprotectin, etc.), and microbiological variables.

The intervention will last 8 weeks and the following visits will be made during the study:

1. Consent- Pre-Randomization Visit

The patient will be evaluated by a doctor from the Gastroenterology service at the University Hospital [name] who will explain the study and evaluate the inclusion and exclusion criteria. Participants will be able to ask all the questions they have about it before signing the written consent. If the potential volunteer wishes to participate, after reading the informative documentation and receiving the relevant explanations, he must carefully read the informed consent and if he agrees with it he must sign it.

The patient will be provided with the 2 containers necessary to collect the stool sample at home for the following visits

2. Baseline Visit (V₀)

The patient will come to the visit with the stool sample corresponding to the basal Visit (V₀) before the intervention.

The demographic variables (age, sex, weight, ethnicity, smoking habit, family history, etc.) will be collected, the different established questionnaires and indexes will be completed (Rome IV, Mayo, IBS-SSS, CVE-20, HADS), and a blood test will be performed (PCR, Calprotectin, blood count, etc.).

The patient will be randomized and the bread will be provided according to the randomization result to intervention A or B. The patient will be told that he can collect the following portions of bread at the centre 1 or 2 times a week, for the next 8 weeks of intervention.

3. End of study Visit (EOS; W8)

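### Sections 3.2, 3.3 and 3.7 give three eligibility rules for quiescent UC that do not agree: Mayo = 2 can be both remission and flare-up, and the calprotectin limit differs 1000-fold in unit

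*Combined protocol and SAP*

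**What the plan says.** The boundary between quiescent and active disease is written three times.

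- Section 3.2 (inclusion): "Remission of ulcerative colitis defined as a total Mayo score ≤ 2 and faecal calprotectin values under 250 ng/g".
- Section 3.3 (exclusion): "Presence of flare-up of UC (Index de Mayo ≥ 2 , Calprotectin ≥ 250 ug/gr". The two conditions are separated by a comma, with neither *and* nor *or*.
- Section 3.7 (methods): "UC in remission (Mayo Index ≤ 2 and Calprotectin ≤ 250 µg/gr".

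Section 3.6 defines the recorded variable as "Faecal calprotectin: faecal calprotectin concentration (µg/g", so its unit matches 3.3 and 3.7 but not 3.2. At the consent visit described in 3.7, the patient sees a doctor "who will explain the study and evaluate the inclusion and exclusion criteria". Nothing in the protocol says which of the three statements governs or how the comma in 3.3 is to be read.

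**The concern.** Both remission definitions admit a Mayo score of 2, while the flare-up exclusion begins at 2. Unless the comma in 3.3 joins the two conditions with *and*, a patient at Mayo 2 with low calprotectin satisfies an inclusion and an exclusion criterion at once. The unit in 3.2 adds a second, independent contradiction, and a value of exactly 250 is handled differently in different places.

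These cut-offs decide who counts as having quiescent UC, which is the population named in the general objective and in all three specific objectives of section 2.2, for example "Assess the impact of traditional bread versus modern bread on improving the clinical response of patients with quiescent UC". Two doctors applying the protocol faithfully could reach different decisions on the same patient. A reader of the results could not tell whether patients at Mayo 2 belonged to the population studied.

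**Working it through.** The plan gives no figure to reproduce here; the check is logical. Let M be the Mayo score and C the calprotectin value in µg/g.

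**Unit.** 250 ng/g ÷ 1000 = 0.25 µg/g, and 250 ÷ 0.25 = 1000. The limit printed in 3.2 is therefore 1000 times lower than the limit in 3.3 and 3.7.

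**Rules as conditions.**

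- 3.2 as printed: M ≤ 2 and C < 0.25
- 3.2 read in µg/g: M ≤ 2 and C < 250
- 3.7: M ≤ 2 and C ≤ 250
- 3.3, comma as *or*: exclude if M ≥ 2 or C ≥ 250
- 3.3, comma as *and*: exclude if M ≥ 2 and C ≥ 250

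**Results for selected patients.**

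| M | C (µg/g) | 3.2 as printed | 3.2 in µg/g | 3.7 | 3.3, *or* | 3.3, *and* |
|---|---|---|---|---|---|---|
| 0 | 100 | fails | meets | meets | not excluded | not excluded |
| 2 | 100 | fails | meets | meets | excluded | not excluded |
| 2 | 249 | fails | meets | meets | excluded | not excluded |
| 0 | 250 | fails | fails | meets | excluded | not excluded |
| 2 | 250 | fails | fails | meets | excluded | excluded |

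**Mayo = 2.** With the comma as *or*, every patient with M = 2 and C < 250 meets 3.7 and is excluded by 3.3. That conflict does not depend on the unit in 3.2. The same patients also meet 3.2 if it is read in µg/g. With the comma as *and*, 3.2 and 3.3 no longer overlap, and 3.3 conflicts with 3.7 only at M = 2, C = 250.

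**Unit conflict.** As printed, 3.2 and 3.7 disagree for every patient with M ≤ 2 and 0.25 ≤ C ≤ 250. For example, 100 µg/g is 100,000 ng/g, and 100,000 ÷ 250 = 400 times the printed limit. If 3.2 is read in µg/g, the two sections disagree only at C = 250.

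**Which reading of the comma is likelier.** The opposite of a rule requiring M ≤ 2 and C < 250 is M > 2 or C ≥ 250, so *or* is the natural connective for an exclusion meant to mirror the inclusion. Under *and*, the exclusion adds nothing to 3.2, because anyone it catches has C ≥ 250 and has already failed 3.2. The other comma-separated lists in 3.3 are also alternatives. None of this proves the intent, but it shows that *or* is not a strained reading.

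**The case against.** Four points can be made against giving this much weight.

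1. The main overlap is conditional: it needs the comma to mean *or*, and for 3.2 it also needs ng/g to be read as µg/g. This is true, and the conclusion is stated with those conditions. However, no reading makes all three sections agree: even under *and* with 3.2 in µg/g, a value of exactly 250 is treated inconsistently.
2. The ng/g is very likely a typing slip, since 3.3, 3.6 and 3.7 all use µg/g. That is a fair point, and the literal reading should not be taken as the practical effect. The slip nevertheless stands in the inclusion criterion itself.
3. By the usual convention a patient must meet every inclusion and no exclusion criterion, so under *or* a patient at Mayo 2 is simply excluded. The protocol does not state that precedence. If it applies, a limit of ≤ 2 in 3.2 and 3.7 misdescribes the patients who can actually enter.
4. No consequence for the results is demonstrated. This stands: the ambiguity arises before randomisation, does not itself bias the comparison between arms and changes no stated statistical figure. The remaining case for correction is that these thresholds decide enrolment, and that Mayo 2 is an ordinary whole-number score at the top of the permitted range rather than a freak value.

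**Conclusion.** The concern holds; the text should be fixed. The eligibility rules are inconsistent as written in three respects.

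- **Mayo = 2 with calprotectin below 250 µg/g:** remission under 3.7 (and under 3.2 in µg/g) and flare-up under 3.3 if the comma means *or*. Under *and*, only the single point of Mayo 2 with exactly 250 µg/g remains in conflict between 3.3 and 3.7.
- **Unit:** the limit in 3.2 is 1000 times lower than in 3.3 and 3.7, whichever way the comma is read.
- **Exactly 250 µg/g:** fails 3.2, meets 3.7 and meets the calprotectin part of 3.3.

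The share of the 96 planned patients affected is unknown, because the documents give no distribution of either measure. The effect is on who is enrolled and on how the quiescent population is reported. Comparing 3.2 with 3.3 assumes that the total Mayo score in 3.2 and the Mayo index in 3.3 are the same score. The conflict between 3.3 and 3.7 does not need that assumption, since both refer to the Mayo index.

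**What to change.** Reconcile 3.2, 3.3 and 3.7 so that they share:

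- one Mayo cut-off, with the Mayo score used named in the same way in each section;
- one calprotectin unit, consistent with 3.6;
- one rule for a value of exactly 250;
- an explicit connective in 3.3, so that no patient can meet both the remission inclusion and the flare-up exclusion.

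Which threshold applies is for the investigators to decide. Any patients already enrolled at Mayo 2 or at the calprotectin limit should be checked against the reconciled rule, and the study population should be reported by that definition.

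The cost is a short amendment to three sentences, with no extra data or patients.

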3.3. Exclusion criteria

- Presence of flare-up of UC (Index de Mayo ≥ 2 , Calprotectin ≥ 250 ug/gr)
- Coeliac disease, colectomy, or intestinal resection
- Antibiotic intake, prebiotic or probiotic treatment within 3 months before the study
- Any malignancy, pregnancy, or breastfeeding
- Intake of medication potentially influencing gastrointestinal function
- Disability to give informed consent

3.4. Interventions

The study intervention will consist of the daily consumption of 200g of one of the two types of study bread, a traditional bread (treatment) and a modern bread (control), for 8 weeks by the participants.

Traditional bread has the following composition: whole-grain wheat flour (stone-ground), water, freeze-dried Paris yeast (<1%), compact sourdough and salt. Fermentation is of the acetic-lactic type for more than 40 hours.

On the other hand, modern bread has the following ingredients: refined flour, water, salt, yeast. With a fast fermentation fully controlled in a maximum of 2 hours.

Elias Forner SL will supply the bread needed for participants' daily consumption at the centres, where patients will collect it 1 or 2 times a week during the 8 weeks of the intervention. All breads will be prepared with identical presentation by Elias Forner SL. All members of the research team will be blinded to intervention allocation.

No dietary or lifestyle intervention (diet, physical activity, etc.) will be carried out in any of the two experimental groups.

3.5. Randomization

Participants will be assigned to one of the two interventions using a random sequence separated by sex. It will remain double-blind throughout the study. In the case of withdrawal or abandonment of a participant, the new subject will be assigned a consecutive number and the intervention he will receive will be assigned using the same random sequence separated by sex as the rest of the participants.

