3.9. Statistical analysis

All statistical analyses will be performed using R software (2.14.0, <http://www.r-project.org/>). Pearson's chi-squared test will be used to determine whether there is a statistically significant difference between demographics and questionnaire data with more than one category. Normality for numerical data will be assessed through the Shapiro-Wilk test. For data with normal distribution, a paired t-test will be used to determine whether there is a statistically significant difference, whereas, for data with non-normal distribution, the Wilcoxon signed-rank exact test will be used. Significance levels will be established for $p \leq 0.05$.

Alpha diversity indices together with beta-diversity matrices will be computed by groups of intervention. Normality will be assessed through the Shapiro-Wilk test, and statistical differences in each treatment group will be analysed using Welch two sample t-test or paired t-test for data with normal distribution and Wilcoxon rank sum exact test or Exact Wilcoxon Signed-Rank test for data with non-normal distribution. For beta diversity matrices, unweighted Unifrac, weighted Unifrac and Bray-Curtis distances will be computed and plotted through principal coordinate analyses (PCoA).

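### Randomisation is stratified by sex, but no planned outcome analysis uses sex; adding it is a free improvement with a gain that is conditional and probably small.

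*Combined protocol and SAP*

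**What the plan says.** Section 3.5 (Randomization): "Participants will be assigned to one of the two interventions using a random sequence separated by sex". A patient who replaces a withdrawal takes the next number, with the arm "assigned using the same random sequence separated by sex as the rest of the participants". No blocks or other restriction within sex are described.

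Section 3.7 (Methods): "The proposed study will include 96 patients with UC in remission", and "These patients will be randomized to one of the two intervention arms (N=48 per group"). Section 3.6 lists sex among the demographic variables, so it is recorded for everyone.

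Section 3.9 (Statistical analysis) names these tests:

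- For categories: "Pearson's chi-squared test will be used to determine whether there is a statistically significant difference between demographics and questionnaire data".
- For numerical data in general: a paired t-test, or a Wilcoxon signed-rank test if the data are not normal.
- For alpha diversity: "statistical differences in each treatment group will be analysed using Welch two sample t-test or paired t-test", with rank-sum or signed-rank tests if the data are not normal.
- For beta diversity: distance matrices and ordination plots, with no test named.

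The section contains no covariate, regression model or stratified test. Section 2.2 (the objectives) includes a comparison of traditional with modern bread on clinical response.

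**The concern.** A factor used to restrict randomisation normally belongs in the analysis. When stratified allocation balances a prognostic factor, chance differences in that factor no longer add to the variability of the arm contrast. An unadjusted two-sample test still counts the variation between the sexes in its standard error. That standard error is then larger than the true one, the p-values are somewhat too large, and some power is given up. What is at stake is precision in a trial of 48 patients per arm; the error does not run towards false positives.

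A second matter sits beside it. If the bread comparison is to be made on numerical clinical outcomes, a between-arm model has to be written, and that model is the natural place for sex.

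**Working it through.** **1. The plan's own figure.** The text available gives 96 patients, 48 per arm, without an effect size, SD, power or dropout rate, so that number cannot be reproduced. For a reference difference I invert the usual formula at two-sided 0.05 and 80% power: d = (1.960 + 0.842) × √(2/48) = 0.572 SD. Section 3.9 sets the threshold at 0.05 but does not state sidedness; two-sided is an assumption.

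**2. Which tests have a between-arm standard error?** I read the Welch and rank-sum tests for alpha diversity, and the chi-squared test on questionnaire categories, as comparisons of the arms. Paired and signed-rank tests work on within-patient differences, have no between-arm standard error, and cancel a stable sex difference. The argument therefore does not reach numerical scores such as the IBS-SSS or HADS as their analysis now stands.

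**3. Size under exact balance within sex.** The sex effect is not in the documents. I assume a difference of s within-sex SDs and a proportion p of one sex.

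- Share of variance due to sex: R² = v/(1 + v), with v = s²p(1 − p).
- Unadjusted SE relative to true SE: 1/√(1 − R²).
- True type I error: 2 × [1 − Φ(1.96/√(1 − R²))].
- Unadjusted power: Φ((d − 1.96 × SE₀)/SE₁), and adjusted power: Φ(d/SE₁ − 1.96), where SE₀ = √(2/48) = 0.2041 and SE₁ = SE₀√(1 − R²).

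Example, s = 0.5 and p = 0.5: v = 0.0625, R² = 0.0588, SE ratio 1.031, SE₁ = 0.1980. Type I error is 2 × [1 − Φ(2.020)] = 0.043. Unadjusted power is Φ(0.868) = 80.7% and adjusted power is Φ(0.928) = 82.3%.

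| Sex effect (SD) | R² | SE excess | Type I error | Power, unadjusted | Power, adjusted |
|---|---|---|---|---|---|
| 0 | 0 | 0% | 0.050 | 80.0% | 80.0% |
| 0.2 | 0.010 | 0.5% | 0.049 | 80.1% | 80.4% |
| 0.3 | 0.022 | 1.1% | 0.048 | 80.3% | 80.9% |
| 0.5 | 0.059 | 3.1% | 0.043 | 80.7% | 82.3% |
| 0.8 | 0.138 | 7.7% | 0.035 | 81.8% | 85.5% |

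With 30% of one sex instead of half, the SE excess is 2.6% at 0.5 SD and 6.5% at 0.8 SD. These formulas are for a comparison of means; for the rank-sum and chi-squared tests they indicate direction and rough size only.

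**4. Does it depend on balance within sex?** Simulation used 12,000 trials per setting, 96 patients, half of each sex, and a sex effect of 0.5 SD.

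- Balanced within sex: mean unadjusted SE 0.210, against a true SD of the estimate of about 0.204. Type I error was 0.043 unadjusted and 0.050 adjusted. Power at a difference of 0.57 within-sex SD was 77.2% and 79.2%, a gain of about 2 points.
- Simple randomisation within sex: mean unadjusted SE 0.211 against a true SD of 0.211, type I error 0.047. The unadjusted SE is valid here. Adjusting still lowers it to 0.206.
- With no sex effect, adjusting gains nothing. Under balance the SE is 0.203 either way; under simple randomisation it goes from 0.205 to 0.206.

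**The case against.** The strongest reply is that harm has not been shown. Oversized standard errors need both balance within sex and an outcome that sex predicts, and the documents establish neither. Separate sequences for men and women do not force balance unless each sequence is restricted. The stated 48 per group might suggest restriction, since unrestricted allocation of 96 gives an exact 48/48 split only about 8% of the time (approximately √(2/(π × 96)) = 0.081), but 48 may be only a target and says nothing about balance within sex. Replacements take the next place in the sequence, not the withdrawn patient's arm, so balance among completers is not assured either. The tests concerned cover little of the trial, the error is conservative, and baseline adjustment may absorb part of a stable sex effect, so the gain from adding sex to a model that already has baseline could be smaller than shown.

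All of this stands, and it limits the claim. It does not defend leaving sex out: adjustment helps a little under either allocation method if sex is prognostic, removes chance sex imbalance, and costs almost nothing if it is not.

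A reader might also infer that sex appears in no planned analysis at all. That goes too far, because the chi-squared comparison of demographics can include it. That comparison is descriptive and adjusts no outcome.

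**Conclusion.** The point holds in limited form. Allocation is stratified by sex, and no planned outcome analysis adjusts for or stratifies by it. The consequence is conditional: with balance within sex and a sex effect of up to 0.5 SD, the standard error is at most about 3% too large, type I error is no lower than about 0.043, and under 2 points of power are lost by the formula (about 2 in simulation). At 0.8 SD these become about 8%, 0.035 and 4 points. With no sex effect they are nil. The sex effects, equal numbers of each sex and two-sided testing are assumptions.

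A reader might infer that the between-arm standard errors are too large as a matter of fact, and that precision secured by the design is being thrown away. The documents do not support that: they give no restriction within sex and no sex effect, and without such a restriction the unadjusted standard error is valid. Nor does the point bear on the numerical clinical outcomes as now planned. There the gap is different and larger: only within-patient tests are named, so no between-arm test of these outcomes serves the third specific objective in section 2.2. This is a free improvement, not a threat to validity.

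**What to change.** In section 3.9, name a between-arm analysis that uses sex:

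- For each continuous outcome, fit week-8 value = arm + baseline value + sex, and report the arm coefficient with its confidence interval. This also supplies the missing between-arm test of numerical clinical outcomes.
- Where a rank test is kept, use the van Elteren test stratified by sex.
- For categorical outcomes, use the Cochran-Mantel-Haenszel test stratified by sex.

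In section 3.5, state how allocation is restricted within each sex, or that it is not.

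The cost is plan wording and one degree of freedom for sex in each model. No new data are needed, because sex and the baseline values are already collected.

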The patient will come to the visit, 8 weeks later, with the stool sample corresponding to the final visit (VF) of the study.

The various established questionnaires and indexes will be performed (Rome IV, Mayo, IBS-SSS, CVE-20, HADS, Likert scale), and a blood test will be performed (PCR, Calprotectin, blood count, etc.).

The evolution of the patient's symptoms will be assessed after 8 weeks of the intervention, and a new medical assessment will be carried out.

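### Week-8 data are not requested from participants who withdraw, so the paired clinical analyses rest on completers; adding new subjects restores the total but not the missing outcomes

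*Combined protocol and SAP*

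**What the plan says.** **Withdrawal (3.5).** "In the case of withdrawal or abandonment of a participant, the new subject will be assigned a consecutive number". The newcomer's bread comes from the next place in the sex-specific sequence, not from the leaver's arm. The section does not say what happens to the person who left or to their data.

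**Assessments (3.7).** In both groups, "stool and blood samples will be collected before starting the intervention (Visit 0 - Basal), and then after 8 weeks (Final Visit"). The questionnaires follow the same two time points. The final visit is described for patients in general: "The patient will come to the visit, 8 weeks later, with the stool sample corresponding to the final visit (VF"). There is no interim outcome visit, and those who have withdrawn are not mentioned.

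**Analysis (3.9).** For normally distributed numerical data "a paired t-test will be used to determine whether there is a statistically significant difference"; otherwise "the Wilcoxon signed-rank exact test will be used". Two-sample tests are named only for alpha diversity. The section names no analysis set, missing-data method or sensitivity analysis.

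**Purpose (2.2).** The third objective is: "Assess the impact of traditional bread versus modern bread on improving the clinical response of patients with quiescent UC". The first concerns microbiota "before (V0) and after 8 weeks (VF) of the intake of traditional bread".

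**The concern.** A paired test on V0 and VF silently drops anyone without a VF value. With a single post-baseline visit, a participant who leaves early contributes nothing to the change analysis, and no intermediate score can stand in. Adding a new subject brings the total back up but does not show how the leaver fared.

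If leaving is related to symptoms, the completers are a favourable selection. An arm can then appear to improve with no true change, even when both arms lose the same share. A questionnaire score that was not requested at week 8 may not be recoverable later, so this has to be settled before follow-up ends.

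**Working it through.** **Inputs from the protocol.** 96 patients, 48 per arm (3.7); outcomes at V0 and week 8 (3.7); paired tests at the 0.05 level (3.9). The supplied text gives no dropout rate, effect size, SD or power. There is therefore no figure of the plan's own to reproduce, and 96 is not in dispute here.

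**Assumptions.** True change is zero. Change is standard normal, with positive meaning better. A patient leaves if a latent variable, correlated ρ with change, falls in its lowest fraction q. I use ρ = 0.3, 0.5 and 0.8, and q = 5%, 10% and 20%. Below, z is the q-quantile of the standard normal and φ its density.

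**Step 1: shift in the completers' mean.** Shift = ρ·φ(z)/(1−q).
- q = 0.05: φ = 0.103, and 0.103/0.95 = 0.109; shift 0.03 / 0.05 / 0.09 SD.
- q = 0.10: φ = 0.1755, and 0.1755/0.90 = 0.195; shift 0.06 / 0.10 / 0.16 SD.
- q = 0.20: φ = 0.280, and 0.280/0.80 = 0.350; shift 0.10 / 0.17 / 0.28 SD.

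The implied gap between leavers and completers is the shift divided by q. At q = 0.10 that is 0.6 / 1.0 / 1.6 SD.

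**Step 2: within-arm paired test, 48 randomised, no true change (simulated).**

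| Dropout | ρ = 0 | 0.3 | 0.5 | 0.8 |
|---|---|---|---|---|
| 5% | 0.051 | 0.056 | 0.064 | 0.090 |
| 10% | 0.050 | 0.068 | 0.098 | 0.188 |

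These come from 60,000 replicates. Repeat runs agreed within one percentage point, so I read the ranges as about 5–9% and 7–19%. Replacing leavers until there are 96 completers (blocks of 4 assumed) gives 0.069 / 0.110 / 0.208 at 10% dropout. Replacement does not remove the selection.

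**Step 3: between-arm bias.** This is the difference between the two arms' shifts.
- Equal q and equal ρ: zero.
- 10% versus 5%: ρ × (0.195 − 0.109) = 0.03 / 0.04 / 0.07 SD. Simulated error of a two-sample test of change is 5–6%.
- 20% versus 5%: ρ × (0.350 − 0.109) = 0.07 / 0.12 / 0.19 SD. Simulated error is 6% / 8% / 16%.

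Section 3.9 does not name a two-sample test for the clinical scores, so these error rates describe an analysis the plan would have to add.

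**Step 4: what retrieval would achieve at 20% versus 5%.** If a fraction r of leavers gives week-8 data at random, the remaining shift in an arm is (1−r)·ρ·φ(z)/[1−q(1−r)].
- r = 0.8: 0.2×0.280/0.96 − 0.2×0.103/0.99 = 0.058 − 0.021 = 0.037, so bias is 0.01–0.03 SD.
- r = 0.5: 0.5×0.280/0.90 − 0.5×0.103/0.975 = 0.156 − 0.053 = 0.103, so bias is 0.03–0.08 SD.
- If the worst leavers are the ones who refuse, simulated bias is 0.02–0.05 SD at 80% retrieval and 0.04–0.11 SD at 50%.

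With baseline adjustment but no retrieval (baseline-to-week-8 correlation of 0.5 assumed), simulated bias is still 0.05 / 0.09 / 0.15 SD. Retrieval is therefore the main remedy.

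**The case against.** **The file is incomplete.** Front matter and consent pages were not available and could contain withdrawal terms. This stands, and the point is limited to the supplied text.

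**The quoted sentence is neutral.** A reader might infer that the protocol excludes leavers, or that replacement creates the bias. Neither is supported. Section 3.5 excludes no one, 3.9 never declares a completers-only analysis, and replacement neither causes nor cures the selection. Completers are what remain once paired tests meet a missing second visit. Nor can one infer that everyone who stops the bread is lost: the week-8 visit in 3.7 exempts nobody, so those who stop the bread but stay in the study may already be covered. The gap concerns those who withdraw or abandon.

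**No harm is shown from the documents.** Correct. Rates, reasons and correlations are all assumed. At 5% dropout with a correlation of 0.3 to 0.5 the error rate is close to nominal. If patients who do well are the ones who leave, the bias runs against showing benefit.

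**The randomised comparison is largely protected.** It is tempting to conclude that the bread-versus-bread result is biased. The documents do not support that: allocation is double-blind, the breads look alike, and no differential loss is reported or predicted. Bias there needs dropout, or its link to outcome, to differ by arm.

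**Part of the within-arm problem has other causes.** True. The absence of a between-arm test for the clinical scores, and regression to the mean from the entry rule of "IBS Symptom Severity Score (IBS-SSS) > 175", are separate matters. Dropout can add to them but does not explain them.

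**An estimand is being chosen.** Fair. Scores from people who no longer eat the bread answer a question about allocated bread, and the plan should say so.

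**Conclusion.** The point holds as a gap in data collection and analysis rules, with medium confidence. In the supplied text, nothing requests week-8 data from those who withdraw and nothing keeps them in the analysis, so the paired clinical analyses as written rest on completers.

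Its size cannot be derived from the documents. Under the assumptions above, the within-arm effect ranges from negligible (5% dropout, weak correlation) to roughly a fourfold false-positive rate (10% dropout, correlation 0.8: 19% against a nominal 5%). For the third objective the between-arm bias is nil under equal dropout with an equal link to outcome, and modest unless losses differ clearly by arm. It does not follow that the trial's comparison is invalid. What makes the point worth acting on is that the main remedy is cheap and may not be available afterwards.

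**What to change.** 1. **Sections 3.5 and 3.7.** Ask every randomised participant who stops the bread or leaves, if willing, to complete the week-8 questionnaires. Record the date and reason. Stool and blood from leavers are not required: the first objective concerns microbiota after bread intake, and the assays have a fixed budget (section 6).
2. **Section 3.9, clinical scores.** Compare week-8 values between arms by allocated bread, adjusted for baseline and sex. Keep leavers who have week-8 data in the analysis alongside the added subjects. State that this estimates the effect of allocated bread.
3. **Reporting.** Give withdrawals and reasons by arm, keep completers as a secondary analysis, and add one simple sensitivity analysis for values still missing, for example a tipping point.

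**Cost.** Wording changes, plus about 10 questionnaire sets at an assumed 10% dropout (0.10 × 96 = 9.6). If replacement continues to 96 completers, about 107 are randomised (96/0.90 = 106.7) and the extra sets number about 11. Some leavers will refuse, and the estimate may be less favourable than one from completers.
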